4.7 Accountability Procedures for Investigational Product

Albutein 20% is to be used only for the study in accordance with the directions given in this protocol. The study pharmacist or designee is responsible for the distribution of the IP in accordance with directions given in the protocol and pharmacy manual.

The study pharmacist or designee is responsible for maintaining accurate records of the IP for his/her study center. Investigational product inventory/dispensing documentation verifying the receipt, dispensing, destruction, and return must be maintained and kept current by the pharmacist or designee. The unused inventory must be made available for inspection during the study by the monitor. Any unused material may be destroyed at the center according to their standard operating procedures (SOPs) or may be returned to the sponsor if the study center's SOPs do not allow local destruction.

Unused IP supplies must be accounted for by the monitor and inventory/dispensing logs must be verified by the monitor prior to IP destruction. Written documentation from Grifols or designee of any unused inventory is required. At the end of the study, a copy of the inventory/dispensing log(s) and Interactive Web Response System dispensing documents will be retrieved by the monitor and returned to Grifols.

4.8 Maintenance of Treatment Randomization Codes

Access to the actual randomization schedules or codes must be strictly controlled during the course of the study.

4.9 Data to Be Recorded Directly on the Case Report Forms

Not applicable.

5 SELECTION AND WITHDRAWAL OF SUBJECTS

Eligible participants for this study include male and female adult subjects who are hospitalized with decompensated cirrhosis and ascites without ACLF at Screening. Subjects who fail to meet the eligibility criteria may not be re-screened.

Note that any criterion number containing v5 was modified in the indicated protocol waws modified in the protocol (eg, 2v5 indicates that the original criterion #2 was last modified in Protocol Version 5).

5.1 Inclusion Criteria

Inclusion Criteria:

A subject must meet all the following inclusion criteria to be eligible for participation in this study:

- 1. Male or female subject ≥ 18 years of age.
- 2v5. Subjects with diagnosis of liver cirrhosis (based on clinical, laboratory, endoscopic, and ultrasonographic features or on histology).
- 3v5. Subjects who have been hospitalized for acute decompensation of liver cirrhosis with ascites (or with prior history of ascites requiring diuretic therapy) with or without ACLF at admission or during hospitalization but, without ACLF at Screening.
- 4v5. This criterion has been removed from Version 5 of the protocol.
- 5. In subjects with cirrhosis due to HBV, decompensation must occur in the setting of continuous (no less than 3 months) appropriate antiviral therapy.
- 6. In subjects with cirrhosis due to HCV, only decompensated patients who will not receive antiviral therapy during the study period will be included (subjects receiving antiviral therapy within 14 days prior to enrollment cannot be included in the study).
- 7. In subjects with cirrhosis due to autoimmune hepatitis, decompensation must occur in the setting of continuous immunosuppressive therapy.
- 8. Subjects must be willing and able to provide written informed consent or have an authorized representative able to provide written informed consent on behalf of the subject in accordance with local law and institutional policy.
- 9v5. CLIF-C score > 50 points at screening.

5.2 Exclusion Criteria

A subject meeting any of the following exclusion criteria is NOT eligible for participation in the study.

1v5. Subjects with ACLF at Screening.

87 Ъ 24-Sep-2020 30 Effective Date Page Effective
 Number
 GLB-PRT-ALB-IG1601
 Version
 6.0
 Status
 Errect

 IG1601 - Prevention of Mortality with Long-Term Administration of Human Albumin in Subjects with
 6.0
 Status
 errect
Version 6.0 Decompensated Cirrhosis and Ascites GRIFOLS **Bioscience Industrial Group**

- 2v5. Subjects with type 1 HRS currently on treatment with vasoconstrictors or hemodialysis.
- 3. Subjects with TIPS or other surgical porto-caval shunts.
- 4v5. Subject with refractory ascites as defined by ICA criteria without any other event of acute decompensation (Appendix 2).
- 5v5. This criterion has been removed from protocol Version 5.
- 6v5. Subjects receiving dual anti-platelet therapy or anti-coagulant therapy (exception: DVT prophylaxis).
- 7v5. Subjects with ongoing endoscopic eradication of esophageal varices with ≤ 2 endoscopic sessions completed before screening.
- 8v5. This criterion has been removed from protocol Version 5.
- Subjects with evidence of current locally advanced or metastatic malignancy. Subjects with hepatocellular carcinoma within the Milan criteria [1 nodule ≤5 cm or 3 nodules ≤3 cm] [Appendix 6], non-melanocytic skin cancer, or controlled breast or prostate cancer can be included.
- 10v4. Subjects with acute or chronic heart failure (New York Heart Association [NYHA] Appendix 7).
- 11. Subjects with severe (grade III or IV) pulmonary disease (Global Obstructive Lung Disease [GOLD] Appendix 8).
- 12v5. Subjects with nephropathy with renal failure with a serum creatinine $\geq 2 \text{ mg/dL}$ or systemic hypertension.
- 13v5. This criterion has been removed from protocol Version 5.
- 14. Subjects with severe psychiatric disorders.
- 15. Subjects with a known infection with human immunodeficiency virus (HIV) or have clinical signs and symptoms consistent with current HIV infection.
- 16. Females who are pregnant, breastfeeding, or, if of childbearing potential, unwilling to practice effective methods of contraception (oral, injectable, or implanted hormonal methods of contraception, placement of an intrauterine device (IUD) or intrauterine system, condom, or occlusive cap with spermicidal foam/gel/cream/suppository, male sterilization, or true abstinence*) throughout the study.
 - * True abstinence: When this is in line with the preferred and usual lifestyle of the subject (periodic abstinence [eg, calendar, ovulation, symptothermal, post-ovulation methods], declaration of abstinence for the duration of the clinical study, and withdrawal are not acceptable methods of contraception).
- 17. Subjects with previous liver transplantation.
- 18. Subjects with known or suspected hypersensitivity to albumin.
- 19. Subjects participating in another clinical study within 3 months prior to screening.
- 20v4. Subjects with active drug addiction (exceptions: active alcoholism or marijuana)
- 21. In the opinion of the investigator, the subject may have compliance problems with the protocol and the procedures of the protocol.

- 22. Subjects with ongoing or recent variceal bleeding. (subjects can be included 2 weeks after hemorrhagic episode).
- 23. Subjects with septic shock at screening.
- 24. Subjects with ongoing SBP infection (subjects can be included upon resolution).
- 25. Subjects with current infection of COVID19, those who are less than 14 days post recovery, or those who have clinical signs and symptoms consistent with COVID19 infection.

5.3 Subject Withdrawal Criteria

5.3.1 Screen Failures

Screening evaluations will be used to determine the eligibility of each subject for enrollment into this study. Subjects who fail to meet eligibility criteria during screening evaluations will be considered screen failures and will not participate in the study.

5.3.2 Discontinuation of Subjects from Treatment

If a subject receives a liver transplant, study treatment and all treatment-related assessments will be discontinued upon transplant. The criteria to determine when a subject becomes a candidate for liver transplantation is described in Section 5.3.2.1. The subject will continue to have subsequent planned visit assessment procedures performed.

Discontinuation of the treatment in subjects who receive a TIPS insertion will be at the discretion of the investigators. In case it is decided to discontinue the subject's treatment early, study treatment will be stopped and the subject will continue to have subsequent planned visit assessment procedures performed.

Adverse events that will determine temporary subject's discontinuation from study treatment include the following:

• Subjects developing severe bleeding, Albutein 20% infusions will be temporarily stopped until the bleeding episode is resolved. For subjects with variceal bleeding, Albutein 20% infusions will be temporarily stopped until the subject has received at least 2 banding sessions. Albutein 20% infusions will be resumed after the bleeding episode is resolved or after the subject has received at least 2 banding sessions, respectively.

Adverse events that will determine permanent subject's discontinuation from study treatment include the following:

- Anaphylactic shock or transfusion-related acute lung injury
- Severe AEs (ie, acute myocardial infarction, cerebral hemorrhage, cardiac failure, pulmonary edema, or intestinal necrosis) that precludes the continuation of the subject in the clinical study

Subjects with any one of these severe AEs will be discontinued from study treatment and all treatment-related assessments, and should continue to have subsequent planned visit assessment procedures performed.

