7 ASSESSMENT OF EFFICACY

7.1 Efficacy Variables

7.1.1 Primary Efficacy Variable

• Time to liver transplantation or death through 1 year after randomization.

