9.2 Determination of Sample Size

Based on the CANONIC study, the overall 1-year transplant-free mortality rate in the current study population is assumed to be about 46% (24,26). Assuming a potential drop-out rate of 20% and 5% type-1 error for a 2-sided Chi-square test, a global sample size of 410 patients (205 per treatment group) will allow an 80% statistical power to detect an absolute reduction of 15% (15) for the 1-year mortality rate in subjects treated with SMT + Albutein 20%.

Alternatively, the sample size was calculated based on the log-rank test as follows. Assuming the 1-year transplant or mortality rate is 46% for the control group, or equivalently, the transplant-free survival rate is 54%, which translates to a hazard rate of 0.0017 assuming an exponential distribution. Using a log-rank test at the 2-sided significant level of 5%, a total of 125 events would provide at least 80% power to detect an absolute reduction of 15% in transplant or mortality rate (a 31% 1-year transplant or mortality rate, or equivalently, a 69% transplant-free survival rate) in subjects treated with SMT + Albutein 20%. This absolute difference in transplant or mortality rates translates to a hazard ratio of 0.6022, or an approximate 40% risk reduction. With all subjects followed for the entire 1-year duration of the study, a total of 322 subjects would be required to obtain 125 events. Assuming a dropout rate of 20%, a global sample size of 404 subjects (202 per treatment group) is required. This sample size calculation was performed using Proc Power with the Twosamplesurvival statement in SAS version 9.4.

Taking a conservative approach, the larger of the 2 sample sizes (ie, the one based on the Chi-square test) will be used to ensure the study has sufficient power.

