9.3.2 CLIF-C OF Score and Sub Scores for Organ Function

CLIF-C OF score is evaluated monthly through Month 12 and will be listed.

The CLIF-C OF score system consists of six sub-scores for liver, kidney, brain, coagulation, circulatory, and respiratory organs/systems – each with values of 1, 2 or 3 with a higher number representing more severe disease. Each CLIF-C OF sub-score will be summarized as a categorical variable by treatment for each visit.

The total CLIF-C OF score is a discrete numeric value in the range of 6 to 18 (inclusive) and is defined as the sum of the six organ/system sub-scores. If an individual sub-score is missing, the total score will also be missing. The total CLIF-C OF score and change in total score from baseline to each scheduled post-baseline visit will be summarized, as a continuous variable, by treatment and scheduled visit. In addition, the total score change from baseline of scheduled visits for both treatment groups will be analyzed by MMRM, which includes change in total score from baseline as the dependent variable; treatment, visit, region (Europe or North America) and history of hospitalization for acute decompensation of liver cirrhosis (yes or no), treatment-by-visit interaction, region-by-visit interaction, and history of hospitalization for acute decompensation of liver cirrhosis-by-visit interaction as fixed effects; baseline and baseline-by-visit as covariates; and measures within-subject at each visit as a repeated measure. The model employs an unstructured covariance matrix for the within-subject dependence. If the model fails to converge, the mixed effects model with a compound symmetry correlation structure will be used.

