9.3.4 MELD Score

The Model for End-stage Liver Disease (MELD) score is a continuous numeric value in the range of 6-40, with a higher number representing more severe disease, and is defined as:

$$\text{MELD} = 9.57 * \text{Ln}(\text{Creatinine } \{ \text{mg/dl} \}) + 3.78 * \text{Ln}(\text{Bilirubin } \{ \text{mg/dl} \}) + 11.2 * \text{Ln}(\text{INR}) + 6.43.$$

MELD scores are evaluated monthly through Month 12 and will be listed. If any of the individual clinical parameters used to derive the MELD score report results <1, the result is imputed to 1, and then used to generate the MELD score.

The MELD score will be summarized as a continuous variable. The MELD total score and change in total score from baseline to each scheduled post-baseline visit will be summarized, as a continuous variable, by treatment and scheduled visit. In addition, the MMRM analysis of CLIF-C OF scores will be repeated for the change from baseline total scores

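### Scores recorded after liver transplant enter the exploratory repeated-measures models with no stated handling, so a between-arm transplant imbalance can shift MELD, Child-Pugh and CLIF-C OF

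*Protocol*

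**What the plan says.** Protocol 5.3.2 ends study treatment, and all treatment-related assessments, when a subject is transplanted. It does not define that last term. It then says of the same subject: "The subject will continue to have subsequent planned visit assessment procedures performed".

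The planned visits (Protocol 7.2.1.2.2 and 7.2.1.2.4, and Appendix 1) include the CLIF-C OF, CLIF-C AD, CLIF-C ACLF, MELD and Child-Pugh scores on Day 11, monthly, and at Month 12.

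SAP 9.3 analyses the exploratory endpoints in the ITT population. For CLIF-C OF, SAP 9.3.2 says that "the total score change from baseline of scheduled visits for both treatment groups will be analyzed by MMRM". SAP 9.3.4 carries this over to MELD: "the MMRM analysis of CLIF-C OF scores will be repeated for the change from baseline total scores". The same model serves CLIF-C ACLF and AD (9.3.3), the Child-Pugh total (9.3.5), serum albumin and albumin binding capacity (9.3.9), and the EQ-5D-5L index and VAS (9.3.11). Child-Pugh sub-scores use a cumulative logit model in GENMOD (9.3.5). Early discontinuation visits are mapped to scheduled visits for the exploratory analyses (6.1.5, Appendix 4).

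None of these sections excludes, flags or separately models values dated after transplant. SAP 6.1.1 deals only with missing values, and these values are observed. Transplant is recognised elsewhere in the plan. It is an event in the primary variable ("Time to liver transplantation or death through 1 year after randomization", Protocol 7.1.1), and it ends the dose count that defines the per-protocol population (SAP 6.4.3).

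**The concern.** Followed as written, the models mix values from native livers with values from transplanted livers and attribute the average to the randomised arm. One event then counts as a failure in the primary endpoint and may count as an improvement in the supporting scores.

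MELD, Child-Pugh and CLIF-C OF rest largely on bilirubin and INR, with creatinine, albumin, ascites or encephalopathy added. If those values improve after transplant, the arm with more transplants gains on these scores for a reason unrelated to albumin. SAP section 2 says the planned analyses will go into regulatory submissions or manuscripts, so a reader may use the scores to corroborate or question the survival result. What is at stake is the interpretation of exploratory results.

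**Working it through.** **Inputs from the documents**
- MELD formula, with component results below 1 set to 1: SAP 9.3.4.
- MELD of 15 or more is one of the prompts for transplant evaluation: Protocol 5.3.2.1.
- Planned one-year transplant-or-death rates of 46% and 31%, N = 410, 20% dropout: Protocol 9.2.

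**Inputs the documents do not give, assumed here**
- Transplanted share by arm.
- Normalisation of creatinine, bilirubin and INR (1 or below) after transplant.
- MELD of 15 or 20 before transplant.

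**1. The plan's own figure.** The plan has no figure on this point. Its sample size reproduces: a two-sided 5% chi-square test of 46% against 31% at 80% power needs 165 per arm, 330 in total. 330 / 0.8 = 412.5, so 413 against the stated 410. At 205 × 0.8 = 164 evaluable per arm, power is 0.800. The hazard ratio ln(0.69) / ln(0.54) = 0.6022 also agrees. The planned rates are used in step 5.

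**2. Possible fall in MELD.** With all three components at 1, MELD = 9.57 ln(1) + 3.78 ln(1) + 11.2 ln(1) + 6.43 = 6.43. A subject at 15 who normalises falls 15 − 6.43 = 8.57 points. A subject at 20 falls 13.57.

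**3. Shift in the between-arm contrast.** Shift = (difference in transplanted share of assessed subjects) × (fall in score).

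| Gap in share | Fall 8.57 | Fall 13.57 |
|---|---|---|
| 0 points | 0 | 0 |
| 2 points | 0.17 | 0.27 |
| 5 points | 0.43 | 0.68 |
| 10 points | 0.86 | 1.36 |

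**4. Simulation.** Repeated-measures model with unstructured covariance, 205 per arm, six visits, no drug effect, 25% other dropout, 150 replicates. Entries are Albutein minus SMT at the last visit, for falls of 8.57 / 13.57. Simulation standard errors are 0.04 to 0.06.

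| Transplanted, SMT / Albutein | Post-transplant values kept | Set aside |
|---|---|---|
| 10% / 10% | +0.04 / −0.01 | +0.03 / +0.06 |
| 10% / 5% | +0.43 / +0.70 | −0.07 / +0.01 |
| 15% / 5% | +0.87 / +1.34 | +0.01 / +0.05 |
| 5% / 10% | −0.47 / −0.64 | −0.05 / +0.02 |

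Lower is better, so the arm with more transplants gains in either direction. Simulated transplants did not depend on severity. The last column therefore confirms the mechanism but does not test whether removal is unbiased when sicker subjects are transplanted.

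**5. Gaps the planned effect could produce.** Suppose a fraction f of events is transplant in both arms, transplanted subjects survive, and dropout is non-differential. The transplanted share of those alive at Month 12 is f·p / (1 − p + f·p), with p = 0.46 for SMT and 0.31 for Albutein.
- f = 0.10: 0.046 / 0.586 = 7.8% against 0.031 / 0.721 = 4.3%; shift 0.30 to 0.48.
- f = 0.25: 0.115 / 0.655 = 17.6% against 0.0775 / 0.7675 = 10.1%; shift 0.64 to 1.01.
- f = 0.40: 0.184 / 0.724 = 25.4% against 0.124 / 0.814 = 15.2%; shift 0.87 to 1.38.

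These shifts would favour SMT.

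**6. Against precision.** Assuming an SD of MELD change of 5 to 7 and 120 assessed per arm at Month 12, SE = SD × √(2/120) = 0.65 to 0.90. The 5-point-gap shift of 0.43 to 0.68 is then about 0.5 (0.43 / 0.90) to 1.05 (0.68 / 0.65) standard errors.

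**The case against.** The strongest reply has four parts.

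*The number of post-transplant scores is unknown.* The protocol also stops treatment-related assessments at transplant. If that term covers the severity scores, few such values would exist. Subjects who leave the study supply only transplant and vital-status data afterwards (Protocol 7.2.1.4). This stands in part. The schedule and the continued-visits sentence favour the reading that scores continue, but the undefined term needs settling.

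*The direction is not general.* A reader might infer that the arm with more transplants must look better on every score, or that the exploratory results will contradict the primary. The documents support neither inference. CLIF-C AD contains no bilirubin, ascites, encephalopathy or albumin, and CLIF-C ACLF adds age and white cell count to the OF score. In CLIF-C OF, vasopressor use scores 3 and ventilation generally does too, so a visit soon after surgery could be worse. No transplant rates by arm are given. If more Albutein subjects survive to be transplanted, the shift reverses. This objection stands.

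*Keeping all ITT data is legitimate.* It amounts to a treatment-policy approach. That is fair, but the SAP does not declare it. Setting values aside is not neutral either. A reader might infer that it yields a while-transplant-free result. Inside an MMRM, the removed values are treated as missing at random, so the target is a hypothetical setting without transplant. Because evaluation is prompted by MELD, Child-Pugh, renal worsening or rapid decompensation (Protocol 5.3.2.1), that assumption is doubtful. Death truncates the same scores, and the filter leaves that untouched.

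*The endpoints are exploratory.* They lie outside the fixed sequence in SAP 6.5. This stands, and it limits the consequence.

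**Conclusion.** The gap is real. Post-transplant values enter the exploratory models and the SAP does not say what is being estimated. The shift is conditional: it needs unequal transplant shares and improvement in liver-dependent values after transplant. On those assumptions MELD moves by about 0.4 to 0.7 points for a 5-point gap, and by about zero for equal shares. That is material to a reading of the MELD contrast but, on the assumed precision, not large against its standard error.

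The direction is claimed only for MELD, Child-Pugh and CLIF-C OF. It is uncertain for CLIF-C AD and CLIF-C ACLF, and none is claimed for serum albumin, binding capacity or EQ-5D-5L, which share the same gap. A reader might go further and infer that the trial's efficacy conclusion is biased. The documents do not support that, because no primary or secondary analysis uses these models and type I error is unaffected.

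**What to change.** In SAP 9.3:
- Analyse the severity scores (including Child-Pugh sub-scores), serum albumin, albumin binding capacity and EQ-5D-5L with values dated on or after transplant set aside, including values from mapped early discontinuation visits. Name this as a hypothetical (no-transplant) estimand under missing at random.
- Keep the all-observed-data analysis beside it, named as treatment policy.
- List post-transplant values separately, and show transplant counts by arm and visit.
- In 9.3.1, count ACLF only up to transplant.

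In Protocol 5.3.2, state which assessments the term treatment-related assessments covers, so that it is clear which scores continue.

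The cost is SAP wording, a date filter and a second run of each model. The downside is fewer late observations and dependence on a missing-at-random assumption that severity-driven transplant makes doubtful. That is why both analyses should be shown.

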5.3.2.1 Liver Transplantation Criteria

To confirm that a subject meets the criteria for a liver transplant, the MELD score and the Child Pugh score (Appendix 3) will be assessed. Priority status will be defined by the MELD score and should be considered once a subject with cirrhosis experiences an index complication such as ascites, HE, variceal hemorrhage, and/or hepatocellular dysfunction. Subjects with an index complication and a MELD score ≥ 15 , a Child-Pugh score of ≥ 7 , worsening renal dysfunction, or other evidence of rapid hepatic decompensation should be promptly evaluated for a liver transplant.

Additional criteria for liver transplantation in subjects with hepatocellular carcinoma or worsening within the Milan criteria (Appendix 6) with no CONTRAINDICATIONS as determined by the Organ Procurement and Transplantation Network (OPTN) Dynamic Imaging criteria (31) are as follows:

- Subject is not a candidate for total resection
- The hepatocellular carcinoma meets the definition of a Stage T2 lesion(s) that includes any of the following:
 - One lesion $\geq 2 \text{ cm}$ and $\leq 5 \text{ cm}$
 - Two or 3 lesions ≥ 1 cm and ≤ 3 cm
 - No macrovascular involvement
 - No identifiable extrahepatic spread of tumor to surrounding lymph nodes, lungs, abdominal organs, or bone

